8.2 Classification of Adverse Events

8.2.1 Assigning Severity Rating for Adverse Events

8.2.1.1 Criteria for Determining Adverse Event Severity

The Investigator will make an assessment of the severity of each AE and SAE according to the National Cancer Institute CTCAE, v. 5.0, 2017. For terms not specified with the CTCAE, the criteria in Table 5 should be used to determine the grade severity.

Table 5: Criteria for Determining the Grade/Severity of Adverse Event Terms Not Specified by the National Cancer Institute CTCAE

Grade	Criteria
1	Mild; asymptomatic or mild symptoms, clinical or diagnostic observations only; intervention not indicated
2	Moderate; minimal, local, or noninvasive intervention indicated; limiting age-appropriate instrumental activities of daily living ^a
3	Severe or medically significant but not immediately life threatening; hospitalization or prolongation of hospitalization indicated; disabling; limiting self-care activities of daily living ^b
4	Life threatening consequences; urgent intervention indicated
5	Death related to adverse event

a. Instrumental activities of daily living refer to preparing meals, shopping for groceries or clothes, using the telephone, managing money, etc.

b. Self-care activities of daily living refer to bathing, dressing and undressing, feeding self, using the toilet, taking medications, and not bedridden.

CTCAE = Common Terminology Criteria for Adverse Events.

AE severity should be recorded in the appropriate section of the AE CRF and in the subject's source documents.

8.2.1.2 Toxicity Management Criteria

8.2.1.2.1 Grade 1 or Grade 2 Adverse Event

Subjects who develop a Grade 1 or Grade 2 AE may continue investigational product at the discretion of the Investigator. Subjects who choose to withdraw from study due to a Grade 1 or 2 AE should have study withdrawal/early termination evaluations completed.

8.2.1.2.2 Grade 3 Adverse Event

Subjects who develop a Grade 3 AE should be managed as follows:

- If the Investigator has compelling evidence that the Grade 3 AE has not been caused by investigational product, then dosing may continue after discussion with the Medical Monitor.
- Subjects who develop a Grade 3 AE that the Investigator considers related to investigational product should have the investigational product discontinued. Subjects experiencing Grade 3 AEs requiring permanent discontinuation of investigational product should be followed weekly until resolution or stability of the AE and encouraged to have withdrawal study evaluations completed.

8.2.1.2.3 Grade 4 Adverse Event

Subjects who develop a Grade 4 AE should have investigational product permanently discontinued.

Subjects experiencing Grade 4 AEs requiring permanent discontinuation of investigational product should be followed weekly until resolution or stability of the AE and encouraged to have withdrawal study evaluations completed.

8.2.1.2.4 Folliculitis

Subjects using tapinarof topically may experience folliculitis. The majority of these events are mild or moderate and do not require intervention or interruption in study drug use. On close inspection, the morphology is similar to that of keratosis pilaris suggesting that the potential mechanism may be increased follicular cornification with subsequent follicular plugging. Importantly, AhR regulates the epidermal differentiation complex and tapinarof has been shown to repair the skin barrier through activation of stratum corneum components including fillagrin, hornerin and involucrin. This latter point suggests that the keratosis pilaris-like reaction may be an on-target effect predictive of a therapeutic response to tapinarof cream.

Several approaches can be employed to manage those patients with folliculitis who may be symptomatic including temporary interruption of study drug use at sites of folliculitis and/or the local application to affected areas of topical keratolytics such as 12% lactic acid lotion or 5-10% urea creams or lotions.

8.2.1.2.5 Other Management Criteria:

The Medical Monitor should be notified if any of the following occur:

- Severe signs or symptoms, or significant changes in any of the safety assessments, that put the safety of the subject at risk (e.g., laboratory tests or vital signs, etc.) as judged by the Investigator.

8.2.2 Assigning Causal Relationship to Study Drug

The Principal Investigator or sub-Investigator is to make the causality assessment. The reasonable possibility of the relationship of an AE to study drug is to be assessed with careful medical consideration at the time of evaluation of an AE. The following definitions are to be used for the relationship of the AE to study drug:

- **Related:** A clinical event, including laboratory test abnormality, with a temporal relationship to study drug administration that makes a causal relationship plausible, unlikely attributed to concurrent disease or other drugs or chemicals, and that follows a clinically reasonable response on re administration (rechallenge) or withdrawal (dechallenge), although information on drug withdrawal may be lacking or unclear.
- **Not related:** A clinical event, including laboratory test abnormality, with a temporal relationship to study drug administration that makes a causal relationship improbable and/or in which other drugs, chemicals, or underlying disease provide a plausible explanation.

Any AEs /SAEs assessed as related to study participation (e.g., protocol mandated procedures, invasive tests, or change in existing therapy) or related to study drug will be recorded from the time a subject consented to participate in the study up to and including any follow-up contact.

All AEs, whether related to study drug or not, must be fully and completely documented on the AE page of the CRF and in the subject's clinical record. In the event a subject is withdrawn from the study because of an AE, the primary reason for withdrawal (i.e., due to an AE) must be recorded on the CRF as such.

8.3 Time Period and Frequency for Event Assessment and Follow-Up

8.3.1 Adverse Event Reporting

All AEs will be collected from the time of signed informed consent until the final visit.

Any AEs assessed as related to study participation (e.g., protocol mandated procedures, invasive tests, or change in existing therapy) will be collected from the time a subject consented to participate in the study up to and including any follow-up contact.

All SAEs will be recorded on the CRF and reported to the Sponsor within 24 hours via email or phone (refer to [Medical Monitor / Sponsor Information Page](#) for contact information) (see Section 8.4).

8.3.2 Follow-Up of Adverse Events

After the initial AE/SAE report, the Investigator is required to proactively follow each subject at subsequent visits/contacts. All SAEs and nonserious AEs will be followed until resolution, until the condition stabilizes, until the event is otherwise explained, or until the subject is lost to follow-up.

The Investigator will assess the outcome of each AE using the following criteria:

- **Recovered/Resolved:** The event has improved or subject recuperated.
- **Recovered/Resolved with sequelae:** The subject has recuperated but retained pathological conditions resulting from the prior disease or injury.
- **Recovering/Resolving:** The event is improving.
- **Not recovered/Not resolved:** The event has not improved or subject recuperated.
- **Unknown:** The outcome of the event is not known, not observed, not recorded, or refused.
- **Fatal:** Termination of life as an outcome of the AE.

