14. A history of or ongoing serious illness or medical, physical, or psychiatric condition(s) that, in the Investigator's opinion, may interfere with the subject's participation in the study, interpretation of results, safety of the subject or ability to understand and give informed consent.
15. Known hypersensitivity to tapinarof or excipients.

Investigational Product, Dosage and Mode of Administration:

Tapinarof cream, 1% is a white to off-white cream containing 1% weight/weight (10 mg/gram) tapinarof, supplied in 30-gram tubes, and is to be administered by the subject or their caregiver OD via topical application of a thin layer to affected areas.

Reference Therapy, Dosage and Mode of Administration:

Not applicable.

Duration of Treatment:

Subjects enrolling in this study may receive treatment for up to 48 weeks. The duration of treatment is based on the vIGA-AD™ score. The end of the study is defined as when the last active subject has completed the Follow-up Visit.

Criteria for Evaluation:

Criteria for Evaluation:	
Efficacy Assessments:	
 • vIGA-AD™ • Eczema Area Severity Index (EASI) • Percentage of total body surface area (%BSA) affected
Functional Outcomes and Quality of Life Assessments:	
 • PP-NRS, for completion by subjects ages \geq 12 years and for completion by caregivers of subjects ages < 12 years • [REDACTED] • [REDACTED] • [REDACTED] • [REDACTED]
Safety Assessments:	
 • AEs • Vital signs • Physical examinations • Clinical laboratory tests • [REDACTED]
Study Endpoints:	
 • Incidence, frequency, and duration of treatment-emergent AEs and SAEs • Change from Baseline in laboratory values • Change from Baseline in vital signs • [REDACTED] • [REDACTED] • [REDACTED] 
 ○ [REDACTED] ○ [REDACTED] ○ [REDACTED] • [REDACTED] 
 ○ Proportion of subjects who achieve vIGA-AD™ = 0 at least 1 time during the study ○ [REDACTED]

- For subjects entering the study with a vIGA-AD™ score ≥ 2 :
 - Proportion of subjects who achieved vIGA-AD™ = 0 or 1 at least 1 time during the study
 - [REDACTED]
- The following endpoints will be summarized over subjects in the intent-to-treat (ITT) population:
 - [REDACTED]
 - [REDACTED]
 - [REDACTED]
 - [REDACTED] change and percent change from Baseline in %BSA affected by visit (OC and LOCF).
 - [REDACTED]

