6.2.4 Clinical Safety Laboratory Assessments

All protocol-required laboratory assessments must be conducted in accordance with the Study Reference Manual or Laboratory Manual and the protocol Schedule of Assessments ([Table 1](#)). Laboratory requisition forms must be completed, and samples must be clearly labeled with the subject number, protocol number, site number, and visit date. Details for the preparation and shipment of samples will be provided by the laboratory and are detailed in the Study Reference Manual or the Laboratory Manual. Reference ranges for all safety parameters will be provided to the site by the laboratory responsible for the assessments.

A list of clinical laboratory tests and parameters is provided in [Table 3](#).

All laboratory tests with values that are considered clinically significantly abnormal during participation in the study should be repeated until the values return to normal or Baseline. If such values do not return to normal within a period judged reasonable by the Investigator, the etiology should be identified, if possible, and the Sponsor and Medical Monitor notified.

Table 3: Laboratory Tests

Diagnostic Tests		

• All subjects
• Urine pregnancy tests (WOCBP only)^a• Direct-Enrolling Subjects Only
• Serum pregnancy test at Screening (WOCBP only)• HBsAg• Hepatitis C antibody• Anti-HBc• Anti-HBs^b• At the Investigator's discretion, subjects may be screened for alcohol and illicit drug use.		
Serum Chemistry		

• BUN• Creatinine• Glucose (fasting not required)• Sodium• Potassium• Chloride	
• Total carbon dioxide• Calcium• AST• ALT• Alkaline phosphatase	
• Uric acid• Total bilirubin (+fractionated if required)• Total protein• Albumin
Hematology		

• Platelet count• RBC count• WBC count (absolute)• Reticulocyte count• Hemoglobin• Hematocrit	
• RBC Indices:
• MCV• MCH• MCHC• Reticulocyte percentage	
• WBC Differential:
• Neutrophils• Lymphocytes• Monocytes• Eosinophils• Basophils

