8.1.3 Adverse Events of Special Interest

In prior clinical studies, contact dermatitis, folliculitis, and headache have been identified as AEs of particular clinical importance and will be reported as AESIs in this study whether or not the AE is considered related to study drug.

In each case study drug may be continued or discontinued, based on Investigator judgment, and may be restarted when the event resolves. In addition, the following information must be collected for each of these AESIs:

Contact Dermatitis

Contact dermatitis: the study site should collect location, duration, size, associated symptoms (itching, burning, pain), severity (mild, moderate, severe), time to onset, and photograph the affected site (if possible). If the subject or caregiver contacts the study site to report significant skin irritation at or near the site of study drug application between study visits, the subject should be brought in for an unscheduled visit, if possible.

Headache

The study site should collect duration, severity (mild, moderate, severe), time to onset, and location (e.g., frontal, temporal, occipital, diffuse).

Follicular Event

The study site should collect the location, duration, size, associated signs and symptoms (itching, burning, pain, erythema), severity (mild, moderate, severe), describe morphology [scale (keratotic/cornified) or no scale (non-keratotic/non-cornified)], time to onset, and photograph the affected site (if possible). Additional information regarding management of folliculitis is provided in Section 8.2.1.2.4.

In particular, the term ‘folliculitis’ may not correctly describe the morphology of the observed local follicular events as these appear to be more consistent with a keratoses pilaris-like follicular based papule. Tapinarof upregulates components of the stratum corneum, including involucrin, hornerin, and filaggrin and increased cornification at, and subsequent mechanical occlusion of, the follicular ostia has been suggested to be a potentially on target mechanism by which these lesions may develop in some individuals treated with tapinarof cream. Additional morphologic description will help to more fully and appropriately characterize these follicular events.

Possible descriptors include, but are not limited to:

- Folliculitis
 - Non-inflammatory
 - Inflammatory
- Milia
 - Non-inflammatory
 - Inflammatory
- Keratosis pilaris
 - Non-inflammatory

- Inflammatory

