For each of these categories, TEAEs will be summarized by SOC in alphabetical order and PT in descending order of frequency. TEAEs ongoing at the end of the previous studies will be considered in the first category (i.e., day of onset ≤ 12 weeks).

At each level of summarization, a subject will be counted once if he/she reported one or more events. The severity of TEAEs and relationship to study drug will be summarized in a similar manner. For summaries of relationship to study drug, a subject will be classified according to related or not related. For summaries of TEAE CTCAE grade, a subject will be classified according to the worst grade.

For treatment-emergent AESIs, summarization will be more extensive, reflecting the more detailed information collected. Information summarized will include number of events per subject, earliest onset day, duration (in days), causality, grade and seriousness of AESIs, outcome, actions taken, assorted physical characteristics of the AESIs, and demographic/baseline characteristics and vIGA-AD™ status of the subjects experiencing them. Each type of AESI will be summarized separately. If a subject has more than one treatment-emergent occurrence of an AESI, the subject's maximum duration, highest levels of causality and seriousness, maximum grade and generally the most extreme level of each characteristic will be summarized. If an AESI was ongoing at end of study (EOS), it will not be included in the duration summary. AESIs ongoing at the end of previous studies will also be included in the summary.

A Kaplan-Meier figure will be generated for each AESI of time to first event for events starting during the study. Time to first onset will be computed as Onset Date of First Occurrence – Date of Visit 1 + 1 if onset date is on or after visit 1 date. Otherwise, time to first onset will be computed as Onset Date of First Occurrence – Date of Visit 1. Subjects not experiencing the AESI will be censored at the date of study completion or discontinuation. AESIs ongoing at the end of the previous studies will not be included.

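### Section 8.3.2 lets an adverse event that has improved but is still present be coded Recovered/Resolved, so reported outcomes, and possibly durations, can look better than they are

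*Protocol*

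**What the plan says.** Protocol Section 8.3.2 asks the investigator to assign each adverse event one outcome from a list. Three of the definitions matter here:

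- Recovered/Resolved: "The event has improved or subject recuperated".
- Recovering/Resolving: "The event is improving".
- Not recovered/Not resolved: "The event has not improved or subject recuperated".

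A fourth category, resolved with sequelae, rests on recuperation alone and does not mention improvement.

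The same section sets the follow-up rule: "All SAEs and nonserious AEs will be followed until resolution, until the condition stabilizes, until the event is otherwise explained". Loss of contact with the subject is the remaining end point. Section 8.2.1.2 asks for weekly follow-up to resolution or stability for Grade 3 and 4 events that require permanent discontinuation. Section 8.1.3 says that for AESIs study drug "may be restarted when the event resolves".

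The Synopsis lists as a study endpoint "Incidence, frequency, and duration of treatment-emergent AEs and SAEs", and Protocol Section 2 does the same in near-identical terms. SAP Section 13.2 puts outcome and duration in the listing of all treatment-emergent events and summarises both for each type of AESI. It adds: "If an AESI was ongoing at end of study (EOS), it will not be included in the duration summary".

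**The concern.** The word *or* in the Recovered/Resolved definition makes improvement sufficient without recovery. Not recovered/Not resolved turns on improvement too, so improvement, not disappearance, is what separates resolved from unresolved. A contact dermatitis that has gone from Grade 3 to Grade 1 and is still visible satisfies Recovered/Resolved, arguably satisfies Recovering/Resolving, and is shut out of Not recovered/Not resolved. Two trained sites could code it differently and both comply.

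This is an uncontrolled, descriptive study whose first objective is safety and tolerability. Its AESI tables are meant to show how contact dermatitis, follicular events and headache run their course and end. An outcome column that mixes events that are gone with events that have merely eased does not answer that question. There is no comparator arm in which the same coding habit would cancel out.

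**Working it through.** The documents give no figure to reproduce on this point. The check compares the definitions and then follows them into the analyses.

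**1. Is the outcome list mutually exclusive?** Take three states of an event after onset:

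| State of the event | Recovered/Resolved | Recovering/Resolving | Not recovered/Not resolved |
|---|---|---|---|
| Gone | fits | no | no |
| Better, still present | fits (has improved) | fits (is improving) | excluded |
| Unchanged or worse | no | no | fits |

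The middle row fits two categories, and one of them is the resolved category.

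**2. Does another passage repair it?** No visible passage defines resolution or says when an adverse event end date is entered. Protocol Section 6.2.4 does set a return standard: clinically significant laboratory values "should be repeated until the values return to normal or Baseline". That governs repeat testing, not outcome coding, so it neither contradicts Section 8.3.2 nor mends it.

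**3. Where does the outcome code enter the analysis directly?** In the SAP 13.2 listing of all treatment-emergent events and in the AESI outcome summary. Both use the Section 8.3.2 category itself, so this effect does not depend on any end date.

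**4. Where might duration be affected?** The SAP computes days as later date minus earlier date plus 1 (Appendix A), from the event's start and end dates. Let onset be day O, improvement day I and disappearance day G, with O ≤ I < G.

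- End date at disappearance: G − O + 1.
- End date at improvement: I − O + 1.
- Shortfall: G − I days.

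The shortfall arises only if the site enters the end date at improvement. The documents supply no values for I or G, so no percentage can be given.

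**5. The rule for AESIs ongoing at end of study.** It drops only AESIs still present at study end. For those, a site that has closed the event on improvement puts a shortened value into the duration summary, while a site that has left it open has it excluded. An AESI that disappears before study end is not dropped under either practice once its end date is recorded. Where a subject has several occurrences of an AESI, SAP 13.2 takes the longest duration, so not every shortened event moves the table.

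**6. What is not affected.** Grade, causality, seriousness and Kaplan-Meier time to first AESI do not use the outcome category. Nor does the incidence of events starting in the study. For rollover subjects, events resolved before Visit 1 are not counted as treatment-emergent, so the term also touches that rule. The exposure is probably small, because Baseline falls at completion of the parent study's final visit.

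**The case against.** The best defence is context. The definition sits under the label Recovered/Resolved, is paired with recuperation, and stands next to a category for events still improving. A sensible investigator may read has improved as finished and is improving as in progress, and so has a suitable code for a persisting event. That shows correct coding is possible. It does not make the literal reading wrong, and the overlap remains.

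Three stronger readings are tempting, and the documents do not support them:

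- *Durations are in fact times to improvement.* Duration comes from start and end dates, and no passage ties the end date to the outcome code. Protocol Section 11.1.5 treats event start and end dates as source data, and Section 8.1.3 has sites collect AESI duration as its own item, though without saying when it ends. Shortening is possible, not established.
- *Follow-up of persisting reactions ends early because of this definition.* Section 8.3.2 already lets follow-up end when the condition stabilises or is otherwise explained, so it can end with the event still present however resolved is defined.
- *The bias is large.* The documents hold no data on outcomes or durations, and any percentage would rest on assumed dates.

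Two limits also stand. In the visible text only AESIs get a duration summary; for other events duration is a listing field. The annotated CRF and data management plan cited in SAP Section 2 were not available and may say when an end date is entered.

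**Conclusion.** The outcome definition is wrong as written. Applied literally, it allows an event that is still present to be coded as resolved, and it overlaps with the category meant for such events. The direct consequence is in outcome reporting: the resolved share can be overstated, and coding can vary between sites. Confidence in this is high, because it rests only on the wording.

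The effect on duration is conditional. It requires that sites enter the end date when they code an improved event as resolved. If they do, durations of adverse events and AESIs are shortened, and an AESI still present at study end can enter the duration summary instead of being left out. How often this would happen is unknown, and its size cannot be computed from the documents. The point should be corrected, but it does not touch the incidence or severity results for events that start in the study.

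**What to change.** Reword the outcome list in Protocol Section 8.3.2 so that the categories exclude one another:

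- Recovered/Resolved: the event is no longer present, or has returned to the state before the event.
- Recovering/Resolving: the event has improved but is still present; the end date is left open.
- Not recovered/Not resolved: the event is unchanged or worse.

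State in the CRF guidance and in SAP Section 13.2 that the end date used for duration is recorded only when the outcome is Recovered/Resolved, with or without sequelae, or fatal. First check the annotated CRF and data management plan for an existing end-date rule.

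The sponsor must reconcile the uses of resolution and resolves in Sections 8.1.3, 8.2.1.2 and 8.3.2 with the new definition. No restart or follow-up rule is proposed here.

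The cost is three reworded definitions and a short data-entry instruction. Some events will stay open longer, and reported outcomes and durations will look slightly less favourable.
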